TP-PCR	v				v	v	v	v	v
Bacterial STIs	v				v				
RAM	v								

8. Duration of study: Participants will be followed for at least 48 weeks.

9. Primary outcome:

Serologic response at month 6 (defined as either a 4-fold or greater decline in RPR titer compared to baseline or being RPR-nonreactive)

10. Secondary outcomes:

(1) Microbiologic response of syphilis (defined as *T. pallidum* PCR Ct value >38) at week 4

(2) Microbiologic response of bacterial STIs (defined as negative PCR results) at week 4

(3) Serologic response at months 3 and 12

(4) Safety of study treatment recorded by using a diary (all adverse events will be coded and graded according to Common Terminology Criteria for Adverse Events [CTCAE] v4.0.)

(5) Adherence evaluation (the noting of tablet intake in the diary for the 7 days of the treatment period)

11. Futility stopping rules:

(1) In the proof-of-concept phase, microbiologic and/or serologic response of syphilis

(microbiologic response was defined as *T. pallidum* PCR Ct value >38, and serologic response was defined as at least a 4-fold decrease in RPR titers) at week 4 will be compared between study groups. The non-inferiority margin of 10% will be used as the futility stopping rule in the proof-of-concept phase.

(2) Participants with treatment failure at week 24 will receive standard-of-care treatment (BPG 2.4 MU intramuscularly once). Treatment failure is defined as at least a 4-fold increase in RPR titers compared with the baseline RPR or at least a 4-fold increase in RPR titers after achieving serologic response during follow-up. Participants who received additional treatment with an antimicrobial active against *T. pallidum* (i.e. penicillins, third-generation cepheems, doxycycline, or macrolides) will also be excluded from the study.

(3) The continuation phase will be conducted only if microbiologic response of syphilis is non-inferior in the ceftriaxone plus doxycycline group compared with the BPG plus doxycycline group.

Laboratory investigations

1. *T. pallidum* PCR:

T. pallidum PCR will be performed on specimens from oral rinse, urine, rectal sites, blood, and lesions of syphilis. Treponemal DNA will be extracted with the QIAamp DNA mini Kit. The diagnostic PCR assay will be used to amplify the 47 kDa protein membrane gene (*tpp47*).

2. Bacterial STIs screening:

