The screening for bacterial STIs, including *C. trachomatis*, *N. gonorrhoeae*, *Trichomonas vaginalis*, *Mycoplasma* spp., and *Ureaplasma* spp.) will be performed on self-collected specimens from oral rinse, urethral, and rectal sites with the use of multiplex real-time PCR assay on an automated system.

3. Resistance-associated mutation of *T. pallidum*

Single-nucleotide polymorphisms (SNPs) will be determined at positions A2058G or A2059G of the 23S rRNA gene, as well as positions 965–967, 926–928, 939 and 1058 of the 16S rRNA gene.

Statistical analysis

According to the previous randomized controlled, open-label study conducted by Cao Y et al, the serological response of early syphilis at 6 months of follow up was observed in 90.2% in ceftriaxone group and 78.0% in BPG group.¹⁰ Therefore, at least 150 participants would be

required for each treatment group to detect a between-group difference, with a two-sided significance level of 5% and a power of 80%. The intention-to-treat population is defined as all patients who undergo randomization except for those who do not provide consent for the use of their data. The analyses will be performed through the FDA snapshot algorithm in the ITT population, which categorizes outcomes into success, failure, and no data in window. The Categorical variables will be compared by Fisher's exact test or Chi-square test. Non-categorical variables will be compared by Mann-Whitney U test. Factors with P value ≤ 0.2 , or with biological significance will be included for multivariate analysis. Logistic regression analysis will be used to determine the factors associated with serologic responses after treatment. All comparisons will be two-tailed and a P value <0.05 is considered significant. All statistical analyses were performed with the use of STATA software version 17.0 (Stata Corporation, College Station, TX).

References

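### A week-24 treatment failure can be scored as a primary serologic success, and the month-12 coding of re-treated failures is not defined

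*Combined protocol and SAP*

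**What the plan says.** Item 9 (Primary outcome) gives one rule, anchored to baseline: "Serologic response at month 6 (defined as either a 4-fold or greater decline in RPR titer compared to baseline or being RPR-nonreactive". Item 10(3) repeats the outcome later and earlier in follow-up, "Serologic response at months 3 and 12", with no separate definition, so the item 9 definition presumably carries over.

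Item 11(2), under the futility stopping rules, defines treatment failure by two limbs. The first is "at least a 4-fold increase in RPR titers compared with the baseline RPR". The second is "at least a 4-fold increase in RPR titers after achieving serologic response during follow-up". It then states: "Participants with treatment failure at week 24 will receive standard-of-care treatment". Its last sentence begins "Participants who received additional treatment with an antimicrobial active against" T. pallidum, lists penicillins among such drugs, and says that these participants "will also be excluded from the study".

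The Statistical analysis section applies the FDA snapshot algorithm, "which categorizes outcomes into success, failure, and no data in window", to an ITT population of everyone randomized, less only those who withhold consent to use of their data. It does not say whether the snapshot's failure category means the failure defined in item 11(2).

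**The concern.** Response looks at two time points, baseline and week 24. The second limb of failure looks at the path between them. RPR is drawn at weeks 4 and 12, so a response followed by a rise can already be visible at week 24. The same participant can then be a primary responder and a treatment failure at one visit. The snapshot allows one category per participant, and the plan does not say which rule decides.

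Relapse after an initial response is an event that a trial of a single-dose regimen should be able to see in its main outcome. The trial is open-label, so a rule settled late could be settled with allocation known.

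Month 12 raises a second question. By then week-24 failures have been re-treated, yet response is still read against the original baseline, and three codings of these participants are open.

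**Working it through.** **Inputs**
- Response, failure limbs, re-treatment and exclusion: items 9, 10(3) and 11(2).
- RPR at baseline and weeks 4, 12, 24, 36 and 48: item 7.
- Lowest eligible titre 1:4: item 5(1).
- 150 per group: Statistical analysis.
- Assumptions: month 6 is the week-24 visit and month 12 the week-48 visit; nonreactive is given the value 1:1.

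**The plan's own figure.** The 150 is not in dispute and serves here only as a denominator. For 90.2% v 78.0%, two-sided 5% and 80% power, the pooled formula gives 140 per group, the continuity-corrected formula 156, and exact Fisher power 153 (79.2% power at 150). The stated 150 is within 3/150 = 2% of the Fisher figure.

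**Step 1: write the rules as inequalities.** Let B be the baseline titre, L the earlier responding titre from which a rise is measured, and W the week-24 titre.
- Response: W ≤ B/4, or nonreactive.
- Failure, limb 1: W ≥ 4B.
- Failure, limb 2: L ≤ B/4 and W ≥ 4L.

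**Step 2: limb 1 and response.** Both would need 4B ≤ W ≤ B/4, which is impossible. There is no overlap.

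**Step 3: limb 2 and response.** Both need 4L ≤ W ≤ B/4, hence L ≤ B/16. With B = 256, L = 16 at week 12 and W = 64: 256/64 = 4 (response), 64/16 = 4 (failure), and 256/16 = 16 (the 16-fold fall that is required).

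At B = 4, L would have to be at most 0.25, and at B = 8 at most 0.5. With nonreactive valued at 1, neither can occur. Listing all doubling titres, with nonreactive and 1:1 as separate entries:

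| Baseline | (lowest, week-24) pairs meeting both rules |
|---|---|
| 1:4, 1:8 | 0 |
| 1:16 | 2 |
| 1:32 | 5 |
| 1:64 | 9 |
| 1:128 | 14 |
| 1:256 | 20 |

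These are counts of possible courses, not probabilities.

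**Step 4: the reference titre matters.** Limb 2 does not name it. Take 1:256 at baseline, 1:64 at week 4 (256/64 = 4, first response), 1:16 at week 12 and 1:64 at week 24. Measured from the first responding titre the rise is 64/64 = 1, no failure. Measured from the lowest titre it is 64/16 = 4, failure.

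**Step 5: size at month 6.** One participant is 1/150 = 0.67 points in an arm. If 1%, 3% or 5% of an arm had this pattern (assumed; the documents give no rate), 1.5, 4.5 or 7.5 of 150 could be coded either way.

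**Step 6: month 12, one arm.** Let f be the share re-treated and r the share of those who meet the response definition at month 12, with 85% response among the others. All three are assumptions.
- Counted as non-success: (1 − f) × 85%.
- Observed titre used: (1 − f) × 85% + f × r.
- Removed from the denominator: 85%.

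| f | Non-success | Observed titre, r = 50% to 100% | Removed |
|---|---|---|---|
| 2% | 83.3% | 84.3% to 85.3% | 85.0% |
| 5% | 80.75% | 83.25% to 85.75% | 85.0% |
| 10% | 76.5% | 81.5% to 86.5% | 85.0% |

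The coding alone moves the arm by up to f × 100%, that is 2, 5 or 10 points.

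**The case against.** The strongest reply is that item 9 is complete by itself. Treatment failure appears only in item 11(2), as a trigger for re-treatment; no outcome uses it, and the snapshot is not tied to it. On that reading the 256/16/64 participant is simply a responder who is also re-treated, and because re-treatment is set for failure at week 24, it follows the primary measurement. This stands as a description of the literal text. It does not remove the problem: the literal text scores as success someone whom the protocol calls a treatment failure at the same visit, and nothing shows that this was intended.

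A reader might infer three stronger things, which the documents do not support.
- *That re-treated failures do distort month 12.* If re-treated participants are excluded from further follow-up but kept in the ITT population, the snapshot can place them in the no-data category. They then stay in the denominator as non-success and rescue is not credited. This reading is open, though the plan does not state it.
- *That the effect favours non-inferiority.* That would need the pattern to be commoner with ceftriaxone, and no relapse rate by arm is given. A rise may also be reinfection, and item 4 anticipates repeat syphilis. If reinfection hits both arms equally at rate r, counting it as non-response shrinks a true difference d to d(1 − r). For the planning difference of 90.2 − 78.0 = 12.2 points and an assumed r of 5%, that is 12.2 × 0.95 = 11.6. The stricter definition can therefore itself pull the arms together.
- *That it uses up part of a 10-point margin.* Item 11(1) states that margin only for the week-4 proof-of-concept comparison, not for the month-6 outcome.

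**Conclusion.** The concern holds for month 6. Response and second-limb failure are not mutually exclusive, the plan gives no precedence, and as written a declared treatment failure counts as a primary success. The overlap is limited to participants whose titre first falls at least 16-fold, which rules out baselines of 1:4 and 1:8 under the 1:1 convention for nonreactive.

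For month 12 the finding is narrower: the coding of re-treated failures is undefined, and the exclusion sentence and the ITT definition are not reconciled. Distortion is a risk that depends on the rule eventually used, not an established result.

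Size and direction are unknown. The only figure fixed by the plan is 0.67 points per participant in an arm of 150; the other percentages above rest on assumed shares.

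**What to change.** This is an analysis rule only; it says nothing about who should be treated or how.

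1. **Month 6.** State that snapshot success requires the fourfold fall from baseline or a nonreactive RPR, and that the protocol's treatment-failure definition has not been met by that visit.
2. **Reference titre.** Name the titre from which a second-limb rise is measured.
3. **Month 12.** Keep participants re-treated for syphilis failure in the ITT denominator as non-success.
4. **Exclusion sentence.** Reconcile it with the ITT definition, so that leaving the study does not mean leaving the analysis.
5. **Sensitivity analysis.** Report response against baseline only, because some rises after response may be reinfection.

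The cost is a few sentences in the outcome and analysis sections. The RPR results needed are already scheduled, and the sample size is not changed by this point. The downside is that response rates become slightly lower and some reinfections count as non-response.

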In Taiwan, we had experienced epidemics and outbreaks of non-classical STIs predominantly affecting men who have sex with men (MSM) living with HIV, such as shigellosis since 2015, acute hepatitis A during 2015-2017, and acute hepatitis C since 2017.³⁻⁵ In addition, syphilis and gonorrhea have been increasingly reported as notifiable diseases over the past decade, while the incidence of HIV infection has significantly decreased since 2018. To facilitate early detection and treatment of individuals with STIs, we have established regular screening for chlamydia, gonorrhea, and syphilis in people living with HIV (PLWH) and MSM receiving pre-exposure prophylaxis (PrEP) in our hospital. In our prospective study investigating the prevalence of STIs among at-risk PLWH, the prevalence of *Chlamydia trachomatis* and *N. gonorrhoeae* was 24.7% and 12.1%, respectively. Surprisingly, we found high rates of *C. trachomatis* and/or *N. gonorrhoeae* co-infections in PLWH with recent hepatitis C virus (HCV) infection (50%), HBsAg positivity (44%), and early syphilis (36%).⁶ Although *C. trachomatis* co-infections have been reported in 20-42% of individuals with *N. gonorrhoeae* infections, few studies document the prevalence of *C. trachomatis* and *N. gonorrhoeae* co-infections among patients with syphilis and viral hepatitis. However, a recent sub-study nested in a randomized controlled trial comparing the efficacy of single dose versus 3 weekly doses of benzathine penicillin G (BPG) for early syphilis also showed a high rate of sexually transmitted co-infections (27%) in patients with early syphilis, including *C. trachomatis*, *N. gonorrhoeae*, and non-gonococcal urethritis.⁷ The findings highlight the importance of integrating bacterial STI screening and treatment into management of early syphilis.

Benzathine penicillin G (BPG) (2.4 million units [MU] intramuscularly once) has been the recommended treatment for early syphilis, but is not effective for treating *C. trachomatis* and *N. gonorrhoeae* co-infections.⁸ The recurrence of BPG shortages has also created an urgent need to identify other alternative treatment that is as effective as BPG for treating early syphilis. Ceftriaxone and doxycycline have been the alternative treatments for

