early syphilis; in addition, ceftriaxone (500 mg intramuscularly once) is effective for treating *N. gonorrhoeae* infection, and doxycycline (100 mg orally twice daily for 7 days) effective for treating *C. trachomatis* infection.⁸ However, the current suggested dose of ceftriaxone for early syphilis (1 g intramuscularly or intravenously once daily for 10-14 days) is inconvenient as an outpatient treatment option. Ceftriaxone is long-acting, with treponemacidal levels remaining at 24 hours following injection. According to a small clinical trial, single-dose ceftriaxone achieved a serological response similar to that of BPG.⁹ Considering the high rate of sexually transmitted co-infections, combination therapy of single-dose ceftriaxone plus 7-day doxycycline for early syphilis may provide convenience and benefit to treatment of *N. gonorrhoeae* and *C. trachomatis* co-infections at a single clinic encounter. In the present study, we aim to compare the efficacy of ceftriaxone plus doxycycline versus BPG plus doxycycline as the treatment for early syphilis among PLWH.

Methods

1. Study design: randomized controlled, open-label, non-inferiority study

2. Study site: infectious diseases clinics at the National Taiwan University Hospital (NTUH)

3. Study duration: 2022-2025

4. Enrolled criteria:

(1) PLWH aged 20 years or more

(2) PLWH with early syphilis (i.e. primary, secondary, or early latent syphilis), confirmed by a positive rapid plasma reagin (RPR) titer with a reactive *Treponema pallidum* particle agglutination (TPPA) assay.

(3) PLWH has provided informed consent

*A participant with repeated syphilis can be repeated enrolled after signing an informed consent if the previous episode of early syphilis was successfully treated with achieving at least a 4-fold decrease in RPR titers and 48-week follow-up is completed.

5. Exclusion criteria:

(1) PLWH with RPR titers of less than 4

(2) Exposure to antibiotics with activity against *T. pallidum*, such as penicillins, third-generation cepheems, doxycycline, or macrolides, within the preceding 4 weeks

(3) A known or suspected infection other than syphilis requiring additional treatment with an antimicrobial active against *T. pallidum*

(4) A history of intolerance to penicillin, ceftriaxone, or doxycycline

(5) Pregnancy

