6. Study procedures: participants will be randomized in a 1:1 ratio to receive ceftriaxone plus doxycycline or BPG plus doxycycline. Randomization will be stratified by the stage of syphilis and RPR titer at baseline.

Arm 1: single-dose ceftriaxone (1g intramuscularly once) plus doxycycline (100 mg orally twice daily for 7 days)

Arm 2: single-dose BPG (2.4 MU intramuscularly once) plus doxycycline (100 mg orally twice daily for 7 days)

7. Baseline and follow-up testing:

Proof of concept phase: (enrolled 50 participants in each group)

- (1) Questionnaire for socio-epidemiologic characteristics and sexual history at baseline and weeks 24, 48
- (2) Serum RPR at baseline and weeks 4, 12, 24, 36, and 48
- (3) *T. pallidum* PCR (TP-PCR) for self-collected specimens from oral rinse, urethral, and rectal sites at baseline, weeks 1, 2, 3, 4, 12, 24, 36, and 48 (specimens collected in weeks 1, 2, and 3 were optional)
- (4) Bacterial STIs (*C. trachomatis*, *N. gonorrhoeae*, *Mycoplasma genitalium*, *M. hominis*, *Ureaplasma urealyticum*, *U. parvum*) for self-collected specimens from oral rinse, urethral, and rectal sites at baseline and week 4
- (5) Resistance-associated mutations (RAM) of *T. pallidum* and other sexually transmitted bacteria at baseline

	Baseline	Wk1 (±2 days)	Wk2 (±2 days)	Wk3 (±2 days)	Wk4 (±2 days)	Wk12 (±2 weeks)	Wk24 (±2 weeks)	Wk36 (±2 weeks)	Wk48 (±2 weeks)
Questionnaire	v						v		v
Doxycycline compliance record		v							
RPR	v				v	v	v	v	v
TP-PCR	v	v	v	v	v	v	v	v	v
		(optional)							
Bacterial STIs	v				v				
RAM	v								

Continuation phase: (enrolled 100 participants in each group)

- (1) Questionnaire for socio-epidemiologic characteristics and sexual history at baseline and

weeks 24, 48

(2) Serum RPR at baseline and weeks 4, 12, 24, 36, and 48

(3) *T. pallidum* PCR (TP-PCR) for self-collected specimens from oral rinse, urethral, and rectal sites at baseline, weeks 4, 12, 24, 36, and 48

(4) Bacterial STIs (*C. trachomatis*, *N. gonorrhoeae*, *M. genitalium*, *M. hominis*, *U. urealyticum*, *U. parvum*) for self-collected specimens from oral rinse, urethral, and rectal sites at baseline and week 4

(5) Resistance-associated mutations (RAM) of *T. pallidum* and other sexually transmitted bacteria at baseline

	Baseline	Wk1 (±2 days)	Wk2 (±2 days)	Wk3 (±2 days)	Wk4 (±2 days)	Wk12 (±2 weeks)	Wk24 (±2 weeks)	Wk36 (±2 weeks)	Wk48 (±2 weeks)
Questionnaire	v						v		v
Doxycycline compliance record		v							
RPR	v				v	v	v	v	v

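### Excluding participants who receive another *T. pallidum*-active antimicrobial after randomisation is not reconciled with the ITT definition, and either way of applying the rule can bias the month-6 comparison

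*Combined protocol and SAP*

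**What the plan says.** The trial is a "randomized controlled, open-label, non-inferiority study" (Methods 1), and "participants will be randomized in a 1:1 ratio" (Methods 6). The primary outcome is "Serologic response at month 6" (Methods 9), based on RPR, and RPR is scheduled at weeks 4, 12, 24, 36 and 48 (Methods 7).

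Two rules bear on who is analysed:

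- Methods 11(2), on participants who receive a further antimicrobial active against *T. pallidum*, lists penicillins, "third-generation cepheems, doxycycline, or macrolides) will also be excluded from the study".
- Statistical analysis: "The intention-to-treat population is defined as all patients who undergo randomization except for those who do not provide consent for the use of their data". Outcomes are classed by the FDA snapshot algorithm as success, failure or no data in window.

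Three further statements bear on which arm is affected:

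- The Background says that BPG "has been the recommended treatment for early syphilis, but is not effective for treating" chlamydia and gonorrhoea. It describes ceftriaxone as effective for gonorrhoea and doxycycline, given in both arms, as effective for chlamydia.
- Both arms are tested for bacterial STIs at baseline and week 4 (Methods 7).
- Exclusion criterion 5(3) bars entry for "A known or suspected infection other than syphilis requiring additional treatment with an antimicrobial active against" *T. pallidum*.

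**The concern.** Receipt of another antimicrobial happens after randomisation and is not among the exceptions in the ITT definition. No sentence says whether such a participant leaves the denominator, is scored as failure, is scored as no data in window, or is analysed on the observed RPR.

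The choice matters because the trigger may depend on the arm. On the plan's own account of drug activity, gonorrhoea that persists after study treatment is expected mainly in the BPG arm, and third-generation cephalosporins are among the drugs that trigger exclusion. Assignment is open-label, so a further antimicrobial is given with the arm known. The primary comparison could therefore shift for a reason unrelated to syphilis response. If the rule stays open, the handling could also be chosen after the data are seen.

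**Working it through.** The plan gives no exclusion rate, so there is no figure of its own to reproduce. The check takes each reading of the rule in turn.

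**Inputs.** From the plan: BPG response 78.0% and 150 per group (Statistical analysis); gonorrhoea prevalence 12.1% in at-risk PLWH (Background). Assumed:

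- A 10-point margin at month 6. The plan states 10% only for the week-4 proof-of-concept rule.
- Ceftriaxone truly at that margin, 68%.
- Week 24 is the month-6 visit.
- Exclusion shares qB (BPG) and qC (ceftriaxone), unrelated to response in the scoring of reading A.

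**Reading A: withdrawn, kept in the denominator as non-success.** Observed rates are 0.78(1 − qB) and 0.68(1 − qC). The difference, ceftriaxone minus BPG, moves by 0.78·qB − 0.68·qC.

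Example with qB = 5%, qC = 0:

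- BPG falls to 0.78 × 0.95 = 0.741, and the difference moves from −0.100 to 0.680 − 0.741 = −0.061.
- SE = √(0.741 × 0.259/150 + 0.68 × 0.32/150) = 0.0523.
- P(declare non-inferior) = Φ((−0.061 + 0.10)/0.0523 − 1.96) = Φ(−1.21) ≈ 11.2%.

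The table gives this approximation beside the exact binomial probability that the lower limit of the 95% Newcombe interval lies above −10 points.

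| qB | qC | Observed difference | Normal approximation | Exact, Newcombe |
|---|---|---|---|---|
| 0 | 0 | −10.0 points | 2.5% | 2.6% |
| 2% | 0 | −8.4 | 4.9% | 5.0% |
| 5% | 0 | −6.1 | 11.2% | 11.5% |
| 5% | 2% | −7.5 | 7.0% | 7.2% |
| 5% | 5% | −9.5 | 3.1% | 3.2% |
| 12.1% | 5% | −4.0 | 20% | 20% |
| 12.1% | 0 | −0.6 | 42% | 43% |

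Two per cent of 150 is 3 participants; 12.1% is about 18.

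The effect does not need the assumed margin. Take both regimens truly at 78% and use the two-sided 5% comparison of proportions that the plan does specify. The chance of wrongly finding ceftriaxone superior rises from 2.5% to 5.1%, 12.2% and 45.7% at qB = 2%, 5% and 12.1%, with none excluded in the ceftriaxone arm.

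**Reading B: removed from the analysis.** If the removed BPG participants would have responded at rate r, the observed BPG rate is (0.78 − qB·r)/(1 − qB). At qB = 12.1%, qC = 0, by the normal approximation:

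| r | Observed BPG rate | False non-inferiority |
|---|---|---|
| 50% | 81.8% | 0.3% |
| 60% | 80.5% | 0.7% |
| 78% | 78.0% | 2.5% |
| 90% | 76.4% | 5.0% |
| 100% | 75.0% | 8.2% |

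There is no shift when the removed participants resemble the rest of the arm. Otherwise it can go either way.

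**The case against.** **The plan may be consistent.** Exclusion from the study can mean withdrawal from follow-up, with every randomised participant still classed by the snapshot algorithm. That reading fits the ITT definition, and this stands. A reader might infer that the rule both contradicts ITT and biases towards ceftriaxone. The documents do not support the two together: the contradiction needs reading B, and the fixed direction needs reading A.

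**The imbalance is inferred.** A reader might infer that positive gonorrhoea tests lead to ceftriaxone almost only in the BPG arm. No section says how a positive test is managed. The rule also covers penicillins, doxycycline and macrolides given for any reason in either arm, and new infections can arise in both. Criterion 5(3) removes some co-infections before randomisation. It does not remove them all: it concerns infections known or suspected at entry, week-4 positives remain possible, and the week-4 bacterial STI outcome presupposes that co-infected participants are enrolled. An excess in the BPG arm is therefore a sound inference of unknown size.

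**The largest figure is a ceiling.** The 12.1% is a prevalence in at-risk PLWH, not an exclusion rate in this trial, and 43% also needs no exclusions at all in the ceftriaxone arm.

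**Retreated failures.** A reader might take the word also in Methods 11(2) to mean that retreated failures are excluded too. The text does not establish this. It places that retreatment at week 24, the primary time point, so the month-6 result need not be lost.

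**Conclusion.** The point holds in conditional form. Methods 11(2) and the ITT definition must be reconciled, because neither way of applying the exclusion is safe. Removal from the analysis breaks ITT, with bias of unknown sign. Withdrawal scored as non-success keeps ITT but favours ceftriaxone by 0.78·qB − 0.68·qC in the at-margin case whenever the BPG arm loses more.

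Under the second reading and the assumptions above, false non-inferiority goes from 2.6% to about 5% with 2% excluded in the BPG arm only, and to 11.5% with 5%. It is 7% with 5% against 2%, and stays near 3% with 5% in both arms. The 43% figure is an upper illustration, not an expectation. The size rests on an assumed month-6 margin, on no-data outcomes counting as non-success, and on exclusion rates that the plan does not give.

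**What to change.** Replace the exclusion clause at the end of Methods 11(2) with a statement that all randomised participants stay in the scheduled RPR follow-up and in the ITT analysis. In the Statistical analysis section, pre-specify:

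1. Antimicrobial given for an infection other than syphilis: use the observed week-24 RPR.
2. Treatment given for syphilis failure or relapse before the week-24 assessment: non-response.
3. Two sensitivity analyses: all such participants as non-responders, and all such participants removed.
4. Counts and reasons reported by arm.

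This concerns follow-up and outcome classification only, not which treatment anyone receives.

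The cost is wording, since the RPR visits already exist ("Participants will be followed for at least 48 weeks", Methods 8). The downside is that an observed RPR includes the effect of the extra antimicrobial and can raise response in either arm. In the BPG arm that works against a non-inferiority claim; in the ceftriaxone arm it works for one. The sensitivity analyses are there to show whether the conclusion depends on it.

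### The week-4 T. pallidum PCR response that decides continuation has two conflicting specimen lists, no rule for combining sites and no baseline-positive requirement, so the same data can give go or stop

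*Combined protocol and SAP*

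**What the plan says.** **Specimens in the schedule.** In the proof-of-concept phase, Methods 7(3) asks for T. pallidum PCR "for self-collected specimens from oral rinse, urethral, and rectal sites at baseline, weeks 1, 2, 3, 4, 12, 24, 36, and 48", with weeks 1 to 3 optional. The continuation phase names the same three specimens.

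**Specimens in the laboratory section.** Laboratory investigations 1 states for T. pallidum: "PCR will be performed on specimens from oral rinse, urine, rectal sites, blood, and lesions of syphilis". Urethral has become urine, and blood and lesions have been added without visit times. Laboratory investigations 2, on the other bacterial STIs, does match the schedule: "performed on self-collected specimens from oral rinse, urethral, and rectal sites".

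**Response.** Secondary outcome 10(1) defines microbiologic response by "PCR Ct value >38) at week 4". Methods 11(1) repeats the cut-off: "PCR Ct value >38, and serologic response was defined as at least a 4-fold decrease" in RPR titre. Neither names a specimen or says how several Ct values form one result.

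**Continuation rule.** Methods 11(1): "The non-inferiority margin of 10% will be used as the futility stopping rule in the proof-of-concept phase". Methods 11(3): "The continuation phase will be conducted only if microbiologic response of syphilis is non-inferior in the ceftriaxone plus doxycycline group" compared with the BPG group. No confidence level or interval method is given for this decision.

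**The concern.** Each participant has at least three scheduled PCR results at week 4 but only one response status. The plan does not say whether every specimen must exceed 38, whether one specimen is decisive, or whether specimens are counted separately. It does not say how a missing specimen is scored. The snapshot categories in Statistical analysis classify an outcome that is already defined; they do not define it.

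Nor does the plan restrict the outcome to participants with detectable T. pallidum at baseline. Someone enrolled on serology alone, or whose only positive specimen was blood or a lesion, has nothing to clear at the scheduled sites. Applied literally, the cut-off scores that person as a responder under either treatment, which pulls the groups together.

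This outcome controls enrolment of 100 of the 150 participants per group (two thirds of the trial). The trial is open-label, so a rule left open could be settled after results by group are known.

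**Working it through.** **The plan's own figure.** The only calculated figure is 150 per group, for month-6 serologic response (90.2% versus 78.0%, two-sided 5%, 80% power). Fisher's exact test, which the plan names, has 79.3% power at 150 and 79.9% at 152, so the figure reproduces closely. It does not concern the week-4 decision, for which the plan states no response rate, power or error rate.

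**Inputs from the plan.** 50 per group in the proof-of-concept phase; 1:1 allocation; 10-point margin; three scheduled specimens.

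**Assumed.** All week-4 PCR counts and positivity rates; a two-sided 95% interval; go when its lower limit lies above -10 points.

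**1. Dilution by participants with nothing to clear.** If a fraction π of each group is positive at a scheduled site at baseline, and the rest stay above Ct 38 at week 4, then observed difference = π × (difference among baseline-positive participants). With π = 0.5 and a true deficit of 20 points: 0.5 × 20 + 0.5 × 0 = 10 points.

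**2. One dataset, three readings.** Suppose three ceftriaxone participants each have one site at Ct 38 or below (one oral, one urethral, one rectal) and one BPG participant is positive in oral rinse. The Wald lower limit is d - 1.96 × √[p₁(1-p₁)/n + p₀(1-p₀)/n].

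- Oral rinse only, 49/50 versus 49/50: 0 - 1.96 × √(0.000392 + 0.000392) = -0.055.
- All three sites above 38, 47/50 versus 49/50: -0.04 - 1.96 × √(0.001128 + 0.000392) = -0.116.

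| Reading | Ceftriaxone | BPG | Wald | Newcombe | Miettinen-Nurminen | Decision |
|---|---|---|---|---|---|---|
| Oral rinse only | 49/50 | 49/50 | -5.5 | -8.7 | -8.8 | go |
| All three sites | 47/50 | 49/50 | -11.6 | -14.3 | -14.6 | stop |
| Per specimen, clustering ignored | 147/150 | 149/150 | -3.9 | -5.1 | -5.1 | go |

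Limits are in percentage points. If non-inferior meant only a point difference within 10 points, all three rows would be go.

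**3. How often the rules disagree.** Two truly equal groups of 50 were simulated with 2% to 8% positivity per site, comparing a one-site rule with an all-three-sites rule.

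- 95% Wald limit, independent sites: opposite decisions in about 35 to 41% of trials.
- 95% Wald limit, correlated sites: about 15 to 28%, depending on the correlation assumed; weaker correlation falls between the two ranges.
- Point-estimate reading: about 1 to 13%.

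**4. What a baseline-positive denominator does to precision.** With one failure in each group, the lower limit is -9.1 (Wald) or -13.6 (Newcombe) at 30 per group, and -13.5 or -19.1 at 20 per group. With no failures in either group the Wald interval has zero width, while the Newcombe limit is -9.9 at 35 per group and -11.4 at 30.

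**The case against.** The strongest defence is that the schedule governs follow-up and the laboratory list merely names every specimen the assay may be run on, such as a lesion at presentation. That is a natural reading, though the text does not state it. It removes blood and lesions from the week-4 decision, but leaves urethral against urine and supplies no combination rule. All sites negative may be what was intended; it is not written.

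A reader might infer more than the documents support:

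- **That the decision rests on five specimens.** The schedule collects three at week 4, so response rates worked out for five describe a decision the plan does not make.
- **That the site rule moves the result by as much as the margin.** At 5% positivity per site, and with independent sites, response within a group falls from 95.0% on one site to 0.95³ = 85.7% on three. The margin applies to the difference between groups. If both groups shift alike, the expected difference stays zero. The effect on the decision comes through extra failures widening the interval, so its size depends on the interval rule.
- **That residual infection is hidden.** RPR is scheduled at weeks 4, 12, 24, 36 and 48, and both the primary outcome and treatment failure are defined on RPR.

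It also stands that the counts above were chosen to show a flip and that independence between sites in one person is unlikely. Methods 11(1) mentions microbiologic and/or serologic response, so serology might be thought to share the decision. Rule 11(3), which governs continuation, names the microbiologic response only.

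**Conclusion.** The concern holds. The specimen lists contradict each other on the face of the text, and the outcome that decides continuation is not defined at participant level. Two consequences follow. First, participants with nothing to clear at the scheduled sites count as responders and dilute any deficit, by half if half are baseline-positive. Second, one dataset can give go or stop according to the site rule: -5.5 against -11.6 points in the example.

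The dilution argument assumes equal baseline-positive fractions in the two groups and no new positivity among the rest. The flip and the disagreement rates assume week-4 positivity that the plan does not give; they show what is possible and cannot be read as forecasts. Under a point-estimate reading the flip is uncommon. The point should be settled before the week-4 results are examined. It does not touch the definition of the month-6 serologic primary outcome or its sample size.

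**What to change.** 1. Make the two lists agree on urethral or urine, and state that blood and lesion PCR are for baseline description unless the same specimen is retaken at week 4.
2. For the continuation decision, define response per participant as Ct above 38 in every scheduled week-4 specimen, among participants with at least one scheduled specimen at Ct 38 or below at baseline. This restriction uses only baseline specimens, so it keeps the randomised comparison.
3. Count a missing week-4 specimen from a baseline-positive site as non-response, and say how one from a baseline-negative site is handled.
4. Report the all-randomised result as a sensitivity analysis.
5. State the confidence level and interval method compared with the 10% margin. A score-based interval is preferable, since Wald collapses when nobody fails. Align 11(1) with 11(3) on whether serology plays any part.

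**Cost.** Only wording and analysis change; the scheduled specimens are already collected. The price is a smaller denominator, a wider interval and a lower stated response rate. This may matter: with 30 baseline-positive participants per group, a Newcombe limit would give stop even if everyone in both groups cleared (-11.4). The sponsor should therefore estimate the expected baseline-positive number and check that the rule can be met with 50 enrolled per group before adopting it.
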